Research Protocol: A Comparative Study of the Advantages of Water-Separation Circumcision

Study Title: Comparative Evaluation of Hydrodissection circumcision vs. Traditional Circumcision Techniques: A Randomized Controlled Trial

1. Study Objective: The objective of this study is to compare the clinical outcomes and advantages of water-separation circumcision (Group A) versus two traditional circumcision techniques (Group B: "Subcutaneous Tissue Sparing "and Group C: "Non-Subcutaneous Tissue Sparing ") in male patients.

2. Background and Rationale: Circumcision is one of the most commonly performed surgical procedures globally. Several techniques exist, including those that preserve or remove subcutaneous tissues. A newer method, water-separation circumcision, is being introduced as a potential improvement. This study aims to evaluate its effectiveness in terms of complications, healing time, and patient satisfaction, comparing it with traditional circumcision techniques.

3. Study Design: This is a **prospective, randomized controlled trial** designed to evaluate the clinical outcomes of water-separation circumcision (Group A) compared to two traditional circumcision techniques (Group B and Group C).

4. Inclusion Criteria:

- ① Complies with the diagnostic criteria for phimosis, foreskin elongation, and related diseases in the "Chinese Expert Consensus on Phimosis, Foreskin related Diseases";
- ② Preoperative routine examination showed no abnormalities in coagulation, blood routine, electrocardiogram and other indicators;
- ③ No severe genital herpes, gonorrhea, syphilis, glans infection, etc.;
- ④ Complies with the indications for sleeve type circumcision;
- ⑤ The patient or family member is aware of the surgical plan and signs the informed consent form.

5. Exclusion Criteria:

- ① Patients with concomitant urethral malformations, such as hypospadias;
- ② Patients with combined inflammation of the penis, prior penile surgery, severe adhesions, buried penis, and short frenulum of the penis;
- ③ Exclude individuals with combined allergies or allergies to multiple medications;
- ④ Patients with severe physical illnesses such as heart and lung dysfunction who cannot tolerate surgery;

- ⑤ Individuals with cognitive impairments or mental abnormalities;
- ⑥ Diabetes with poor glycemic control;
- ⑦ Age >35 or Age<6.

6. Intervention Groups:

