Randomization will be performed using a computer-generated randomization list, ensuring that each participant has an equal chance of being assigned to one of the three groups. Stratified randomization

will be used to ensure balance across demographic variables (e.g., age, baseline health status). Patients will be blinded to group assignment, and the surgical team will remain unaware of the group allocation to reduce bias.

10. Statistical Analysis:

Data will be analyzed using the **Statistical Package for the Social Sciences (SPSS)** software, version 26 (or newer). The following statistical methods will be applied:

Descriptive statistics (mean, standard deviation, frequency distributions) will be used for demographic data and outcome measures.

Chi-square tests will be used to compare categorical variables (e.g., complication rates between the three groups).

Analysis of variance (ANOVA) will be applied to compare continuous variables (e.g., healing time, pain scores) between groups.

If assumptions of normality are violated, **Kruskal-Wallis tests** (non-parametric version of ANOVA) will be used.

Post-hoc tests (e.g., Tukey's test) will be applied where significant differences are found in the ANOVA. **Kaplan-Meier survival analysis** will be used to assess time to healing (i.e., complete wound closure). **P-values of < 0.05** will be considered statistically

significant. **Confidence intervals (95%)** will be reported for all continuous outcomes.

11. Ethical Considerations: The study will be conducted in accordance with the **Declaration of Helsinki** and will be approved by the Chongqing Jiulongpo Hospital ethics committee. All patients will provide written informed consent prior to participation, and their rights, confidentiality, and well-being will be ensured throughout the study. The clinical trial will be registered in a public database.

12. Timeline:

Study start date: 2019-6-30

Study end date: 2024-2-07

Recruitment period: 3 months

Follow-up period: 1 year after surgery

13. Budget Considerations:

Personnel costs (surgeons, nurses, data managers):

1000 x 96=96000RMB

Materials and Equipment (surgical tools, sutures, bandages, anesthesia)

500 x 96=48000RMB

Statistical and software tools: 1000 RMB

Participant compensation for time and travel:

1000 X96=96000 RMB

Principal Investigator: [[name]]

Study Coordinators: [[name]]

Contact Information: [Department of Urology,

Peking University First Hospital, 86

[name]]

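### Free improvement: randomisation is stratified but no named analysis uses the strata, so precision is forgone if the strata predict outcome

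*Protocol*

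**What the plan says.** Protocol Section 9 (Randomization) describes a computer-generated list with equal allocation to the three groups. It adds that stratification "will be used to ensure balance across demographic variables (e.g., age, baseline health status". The factors are examples only. No levels, cut-points, number of strata or block size are given.

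Protocol Section 10 (Statistical Analysis) lists the methods that will be applied:

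- Continuous outcomes: "Analysis of variance (ANOVA) will be applied to compare continuous variables (e.g., healing time, pain scores) between groups".
- Non-normal data: Kruskal-Wallis, "If assumptions of normality are violated".
- Pairwise comparisons: post-hoc tests such as Tukey's, which "will be applied where significant differences are found in the ANOVA".
- Categorical outcomes: "Chi-square tests will be used to compare categorical variables (e.g., complication rates between the three groups".
- Healing: Kaplan-Meier, which "will be used to assess time to healing (i.e., complete wound closure". No comparison test is attached to it.

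No stratum term, covariate or stratified test appears anywhere in the protocol. Section 10 also promises 95% confidence intervals for all continuous outcomes. Section 5 excludes "Age >35 or Age<6", so patients aged 6 to 35 are eligible.

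**The concern.** Stratified allocation makes the groups alike on the stratifying variables, which takes between-stratum variation out of the group differences. An analysis that leaves out the strata still counts that variation as error. The estimate is then more precise than its reported standard error says.

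Children and adults are pooled here, so age could plausibly relate to operation time, bleeding, healing time and pain, which Section 7 lists as the primary outcomes. With 32 patients per group, any precision that the design makes available is worth using. At stake are wider reported intervals and a lower chance of detecting a real difference than the same data could give.

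**Working it through.** **Inputs from the protocol.** Three groups of 32, 96 in total; alpha 0.05; target power 80%; 10% dropout (Section 8). Stratified allocation (Section 9). Unstratified tests (Section 10).

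**The plan's own figure.** The 96 can be neither confirmed nor refuted, because Section 8 gives no complication rates or effect size. The dropout step alone is compatible: 28 / 0.9 = 31.1, rounded up to 32 per group.

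**Assumptions, none of them in the protocol.** R2 from 0 to 30%; equal-sized strata; allocation balanced within strata, for example by permuted blocks; all 96 patients analysed; total within-group SD of 1.

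**Standard error.** For a difference between two groups of 32:

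- reported by ANOVA without strata: sqrt(2/32) = 0.250
- reported with strata in the model: sqrt(2(1-R2)/32), which at R2 = 20% is sqrt(1.6/32) = 0.224
- ratio: 1/sqrt(1-R2), which at R2 = 20% is 1/sqrt(0.80) = 1.12

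**Power for an illustrative 0.6 SD shift in Group A.** The three group means lie 0.4, -0.2 and -0.2 from their average. The noncentrality is 32 × (0.16 + 0.04 + 0.04) = 7.68 before adjustment and 7.68/(1-R2) after it: 8.08, 8.53, 9.60 and 10.97 at R2 = 5, 10, 20 and 30%. The noncentral F distribution (2 and 92 degrees of freedom) gives adjusted power of about 71, 73, 78 and 84%, against 68% with no adjustment. Simulation with two strata and blocks of 3 agrees.

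**Second set-up.** Four strata and an effect of f = 0.322, chosen because it gives 80% power for 96 patients; 20,000 simulated trials per setting.

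| R2 (assumed) | Interval width ratio | Type I error, unadjusted | Power, 0.6 SD shift: unadjusted / adjusted | Power, f = 0.322: unadjusted / adjusted |
|---|---|---|---|---|
| 0 | 1.00 | about 5% | 68% / 68% | 80% / 80% |
| 5% | 1.03 | 4.5% | 68% / 70-71% | 80% / 82% |
| 10% | 1.05 | 3.4-3.8% | 68-69% / 73-74% | 81% / 84% |
| 20% | 1.12 | 2.4% | 68-69% / 78% | 81% / 88% |
| 30% | 1.20 | 1.3-1.6% | 69% / 84% | 82% / 93% |

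The adjusted test kept its type I error near 5% throughout.

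**Categorical outcomes.** Pearson chi-square against a Cochran-Mantel-Haenszel test, with two equal strata, odds ratios of 0.25, 1 and 2 across the groups, and 40,000 simulated trials per setting:

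| Stratum rates at odds ratio 1 (assumed) | Chi-square power | Stratified power | Forgone |
|---|---|---|---|
| 5% and 15% | 38.2% | 38.7% | 0.5 points |
| 10% and 30% | 69.0% | 71.0% | 2.0 points |
| 5% and 35% | 61.3% | 67.5% | 6.2 points |

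Kruskal-Wallis was not simulated. Kaplan-Meier is an estimator with no test named, so there is no error rate to compute.

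**The case against.** Several objections have force.

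- **The loss is conditional.** It requires strata that predict outcome, and the protocol offers no evidence on that. At R2 of 0 there is no loss, and at 5% it is only about 2 power points. This stands, and the range must start at zero.
- **Baseline health status has little room to vary.** Section 4 requires normal preoperative tests, and Section 5 excludes severe illness and poorly controlled diabetes. This stands. Age carries the argument, and its link to outcome is plausible but not shown.
- **Block allocation is not stated.** If the lists within strata were unblocked, simulated type I error of the unadjusted ANOVA was 5.2, 5.3 and 5.6% at R2 = 10, 20 and 40%. With 4,000 runs the simulation error is about sqrt(0.05 × 0.95/4000) = 0.34 points, so this is close to nominal and shows no conservatism. The condition stands, although the stated aim of ensuring balance makes some form of blocking likely.
- **Adjustment could be left to an SAP.** The SAP is not shown and might add it, and the word ANOVA does not strictly exclude stratum terms. This holds only in part. The protocol names specific methods, describes ANOVA as a comparison between groups, and pairs it with Kruskal-Wallis, which makes the one-way test the natural reading. The mismatch is therefore with something stated, not with a silence.

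A reader might go further and infer that the planned power is eroded, or that the comparison is invalid. The documents support neither. Unadjusted power does not fall as R2 rises, and nothing in Section 8 suggests that the 96 relied on adjustment. What is forgone is a possible gain.

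**Conclusion.** The mismatch between Sections 9 and 10 is clear from the text; its effect is conditional. If the strata are prognostic and allocation is balanced within them, the unadjusted ANOVA is conservative. Over an assumed R2 of 0 to 30%, intervals are 0 to about 20% too wide, and type I error runs from about 5% down to about 1.4%. The power forgone runs from none to about 15 points for a 0.6 SD shift, or about 10 points in the second set-up. For chi-square the forgone power was about 0.5 to 6 points in the scenarios tried.

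The treatment comparison is not biased and false positives are not inflated. This is a free improvement and not a flaw that undermines the trial's conclusions.

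**What to change.** 1. In Section 9, replace the examples with the stratification factors and levels actually used, and state how the list is balanced within strata. Nothing can enter a model until this is fixed.
2. In Section 10, make the primary analysis of continuous outcomes a linear model with group and those factors. Age may be continuous. Take Tukey-type comparisons and 95% intervals from that model.
3. If normality fails, use a stratified rank test of van Elteren type. Use Cochran-Mantel-Haenszel for categorical outcomes, and a stratified log-rank test alongside Kaplan-Meier for healing time.
4. Keep the unadjusted tests as sensitivity analyses.

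The cost is wording in two sections and, where there is one, the SAP. No extra patients are needed. Age must already be known to apply the eligibility limits; whether any other factor was recorded in usable form should be confirmed, because the protocol does not say. Adjustment costs almost nothing if the strata do not predict outcome: power was the same with and without it at R2 = 0. Because Section 12 gives an end date of 2024-2-07, the adjusted analysis should be labelled as a later addition if outcome data have already been examined.

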Group A (Hydrodissection circumcision): This group will undergo the water-separation circumcision technique, where water is used to separate the skin from the underlying tissues before performing the circumcision (HC).

Group B (Subcutaneous Tissue Sparing Circumcision):

This group will undergo a traditional circumcision procedure where the subcutaneous tissue is preserved, aiming for less scarring and quicker healing (sCC).

Group C (Non-Subcutaneous Tissue Sparing Circumcision):

This group will undergo the traditional circumcision procedure in which the subcutaneous tissue is not sparing (uCC).

7. Outcome Measures:

Primary Outcome Measure:

1. operation time

Operative time was calculated by timer.

[Time Frame: 1 day]

2. intraoperative bleeding

The amount of intraoperative bleeding is calculated by weighing gauze before and after operation. 1 milliliter is approximately equal to the weight of 1 gram.

[Time Frame: 1 day]

3. The healing time

The healing time was judged by the doctors based on the observation of the wound and inquiry of the patients during 7-25 days after surgery. We defined complete wound healing as the absence of a scab with a completely epithelialized and dry skin surface based on clinical assessment.

[Time Frame: 7-25 days]

4. Intra-operative pain

Intra-operative pain was graded immediately after the operation while the post-operation pain was graded at 1 week by NRS (Numeric Rating Scale). The scale typically ranges from 0 to 10. 0 indicates no pain, while 10 signifies the most severe pain imaginable.

[Time Frame: 1 day]

Secondary Outcome Measures:

5. other complications

incidence rate

[Time Frame: through study completion, an average of 1 year]

6. patient satisfaction

Patient satisfaction is divided into 5 levels: Extremely dissatisfied, Dissatisfied, Neutral, Satisfied, Extremely Satisfied.

[Time Frame: through study completion, an average of 1 year]

8. Sample Size Calculation:

Given an assumed type I error (α) of 0.05 and type II error (β) of 0.20, a power of 80% is desired to detect a significant difference in the primary outcome (complication rate). Using a conservative estimate based on previous studies of circumcision complication rates, a sample size of 96 patients (32 patients per group) will provide sufficient power to detect differences between the three techniques.

This sample size assumes a 10% dropout rate, so 96 patients will be recruited in total.

9. Randomization:

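### Section 9 claims that the surgical team is blinded, but the arms differ only in what that team does, so the claim cannot hold once surgery starts; whether the outcome assessors know the arm is unstated

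*Protocol*

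**What the plan says.** Protocol Section 9 (Randomization) makes two blinding statements in one sentence. Patients are blinded to their group, and "the surgical team will remain unaware of the group allocation to reduce bias". No time limit is attached to the second statement.

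Section 6 (Intervention Groups) defines the arms as follows:

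- Group A is the technique "where water is used to separate the skin from the underlying tissues before performing the circumcision".
- Group B is a traditional procedure "where the subcutaneous tissue is preserved, aiming for less scarring and quicker healing".
- Group C is the traditional procedure "in which the subcutaneous tissue is not sparing".

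No other difference between the arms is described.

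Section 7 lists healing time as a primary outcome, observed between days 7 and 25: "The healing time was judged by the doctors based on the observation of the wound and inquiry of the patients". It gives a criterion: "We defined complete wound healing as the absence of a scab with a completely epithelialized and dry skin surface", on clinical assessment. For complications, listed in Section 7 as secondary, it gives only an incidence rate and a time frame and names no assessor. Section 8 nevertheless calls the complication rate the primary outcome. The protocol does not say whether the doctors who judge healing belong to the operating team or know the arm.

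**The concern.** The protocol promises a safeguard that its own design rules out. A report that repeats the sentence would claim a blinding that could not have existed.

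The sentence is also the only one that could extend to clinicians. Once it is set aside, nothing in the text keeps knowledge of the technique away from those who judge healing or record complications. Healing is the exposed item among the four listed primary outcomes: operation time is taken by timer, bleeding by gauze weight and pain by patient rating, but healing rests on a doctor's judgement. The document also states expectations that point at this outcome. Section 2 presents the water-separation method as a potential improvement, and Section 6 gives quicker healing as an aim of Group B's technique. An assessor who knew the arm could therefore lean, without intending to, towards calling some wounds healed sooner.

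**Working it through.** **The contradiction.** This part needs no arithmetic, because the protocol gives no figure to reproduce.

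1. Section 6: assignment to A, B or C determines which operation is performed, and nothing else is described as differing.
2. To perform the assigned operation, the operators must know which one it is. While operating they see and carry out the distinguishing step.
3. Section 9 says that the team stays unaware. From the start of surgery this cannot be true.
4. Before surgery it can be true, as allocation concealment. Section 9 does not limit itself to that period.

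**The consequence for assessors.** Section 9 covers two parties, patients and the surgical team. If the doctors in Section 7 are members of the operating team, they know the arm. If they are separate, they may or may not know it. The protocol does not settle which applies.

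**Scale, as an illustration on assumed inputs.** The group size of 32 is from Section 8, and the ANOVA and the 0.05 level are from Section 10. The SD of healing time (3 to 6 days) and the 1-day shift are assumptions; the protocol gives neither.

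Suppose there is no true difference and one arm is called healed s = 1 day early. The arm means then deviate from the grand mean by 2s/3, s/3 and s/3 in absolute value. The sum of squares is (4/9 + 1/9 + 1/9)s² = (2/3)s². The noncentrality parameter is λ = 32 × (2/3) × s² / SD² = 21.33 / SD². The test has 2 and 93 degrees of freedom, and the critical F at 0.05 is 3.094.

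| Assumed SD (days) | λ | False-positive rate |
|---|---|---|
| 3 | 2.370 | 0.254 |
| 4 | 1.333 | 0.159 |
| 5 | 0.853 | 0.117 |
| 6 | 0.593 | 0.096 |

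With no shift the rate is 0.05. No figure is offered for complications, because the protocol gives neither a rate nor an assessor.

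**The case against.** **Section 9 means concealment only.** The sentence stands under Randomization, where concealment is usually described, and the English is loose elsewhere. On this reading the defect is poor wording. That is a fair account of what may have been intended. But the words set no limit in time, sit beside patient blinding and give bias reduction as their purpose, so they need correcting on either reading.

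**Assessor blinding is an omission, not an error.** This stands. A reader might infer that the surgeons judge their own patients' healing, or that the healing results are biased. The documents support neither: the protocol speaks only of doctors, makes no claim about assessor blinding, and gives explicit healing criteria that narrow the room for judgement. The gap counts as a consequence of the false statement, not as a second mistake.

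**The figures do not measure the proven defect.** This also stands. They model an assessor bias that is not shown, with an assumed SD and shift, and the answer depends heavily on the SD. They indicate scale and are not evidence of harm.

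**Patient blinding.** A reader might also infer that inclusion criterion 5, which requires awareness of the surgical plan, contradicts it. That is ordinary consent wording and need not mean disclosure of the assigned arm, so no contradiction follows.

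**Conclusion.** The contradiction is certain and rests only on Sections 6 and 9: the protocol states a blinding of the surgical team that its design cannot provide beyond the start of surgery. It follows that the protocol describes no workable protection of clinician-judged outcomes, namely healing time and, with no assessor named, complications. Whether the assessors know the arm is an open question, so bias is possible and not demonstrated.

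If an assessor bias of 1 day in one arm did occur, the nominal 5% error rate for healing time would become roughly 10% to 25%. That range depends entirely on the assumed shift and on SDs of 6 down to 3 days. The case for correcting Section 9 does not depend on it. The correction should be made; it alters neither the sample size nor the analysis.

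**What to change.** **Section 9.** Remove the claim about the surgical team. If the sponsor confirms that this is what is done, write: *The operating team is not blinded; allocation is concealed from it until the operation.* If concealment ran differently, state what was actually done.

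**Section 7.** Where existing staff allow, have healing judged against the criteria already given by a study doctor who did not operate on that patient and is not told the arm. Do the same for complications where feasible.

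**If that is not possible, or assessments are complete.** The stated end date is 2024-2-07 and part of the outcome text is in the past tense, so this may apply. Claim no blinding of the surgical team or the assessors, describe the trial as at most patient-blinded, and report who judged healing and complications and whether they knew the technique.

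**Cost.** A less favourable blinding label and, if assessments are still to come, a rota constraint on existing doctors. The protocol does not give the number of doctors, so the sponsor must say whether the rota is workable. No patients or visits are added.

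### Section 10 guards only against non-normality: if the techniques differ in spread, pooled-SD pairwise tests are too conservative for the less variable pairs and too liberal for pairs with the most variable arm

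*Protocol*

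**What the plan says.** Protocol Section 10 names the method for continuous outcomes: "Analysis of variance (ANOVA) will be applied to compare continuous variables (e.g., healing time, pain scores) between groups". The one condition for leaving it is "If assumptions of normality are violated", in which case Kruskal-Wallis takes over. On pairwise comparisons it says: "Post-hoc tests (e.g., Tukey's test) will be applied where significant differences are found in the ANOVA". Intervals at 95% "will be reported for all continuous outcomes", but the section does not say whether these are for arm means or for differences, nor whether they use a pooled SD. Healing time also has a Kaplan-Meier analysis.

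Equality of variances is not mentioned and no unequal-variance method is named. The SD appears only as something to be reported descriptively; no value is given for any arm or outcome. Section 8 sets "a sample size of 96 patients (32 patients per group"), and Section 9 gives equal allocation.

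**The concern.** ANOVA has two distributional assumptions for independent groups, normality and equal variance, and Section 10 protects only the first. Tukey's test and other post-hoc tests built on the ANOVA error term use one SD pooled over A, B and C for every pair. The third arm's variability therefore enters a comparison to which it does not belong.

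Unequal spread is plausible here. Operation time, bleeding by gauze weight and the 0-10 pain score all have a floor at zero, and with such measures a lower mean often goes with a smaller spread. If the techniques differ in mean, as the trial hopes to show, they may well differ in SD too. Roughly normal data with unequal SDs would never trigger the fallback, and Kruskal-Wallis does not repair unequal spread in any case.

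The stake lies in the pairwise results, A against B and A against C, which are the stated objective in Section 1. A real difference between two quiet arms can be missed, and a comparison with the noisy arm can look more precise than it is.

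**Working it through.** **Inputs from the protocol.** 32 per arm (Section 8); 1:1:1 allocation (Section 9); α = 0.05 (Sections 8 and 10), taken as two-sided; 10% dropout (Section 8), so 96 × 0.9 = 86.4, about 29 per arm.

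**The plan's own figure.** The 96 cannot be reproduced, because no complication rates are given. Only the dropout step can be checked: 86 / 0.9 = 95.6, rounded up to 96. The point below uses only the 32 per arm.

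**Assumed.** The SDs. Ratios A:B:C run from 1:1:1 to 1:1:3, with other arrangements to show how the direction moves.

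**Step 1: interval width.** With equal n, pooled SE = √[(2/n)(sA² + sB² + sC²)/3] and true SE = √[(si² + sj²)/n]. Their ratio is √[(2/3)(sA² + sB² + sC²)/(si² + sj²)]. Above 1 the interval is too wide; below 1 it is too narrow.

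For 1:1:2 the variances sum to 6. A-B: √[(2/3)(6)/2] = √2 = 1.41. A-C: √[(2/3)(6)/5] = √0.8 = 0.89.

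| SDs A:B:C | A-B | A-C | B-C |
|---|---|---|---|
| 1:1:1.5 | 1.19 | 0.93 | 0.93 |
| 1:1:2 | 1.41 | 0.89 | 0.89 |
| 1:1:3 | 1.91 | 0.86 | 0.86 |
| 1:1.5:2 | 1.22 | 0.98 | 0.88 |
| 1:2:1 | 0.89 | 1.41 | 0.89 |
| 2:1:1 | 0.89 | 0.89 | 1.41 |
| 1:2:2 | 1.10 | 1.10 | 0.87 |

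The exact rule is that a pair's interval is too wide when the third arm's variance exceeds the average of the pair's own two variances, and too narrow when it falls below. With one clearly noisiest arm, the pairs containing it are too narrow. With two noisy arms (1:2:2), only the pair made of both is.

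**Step 2: Tukey coverage and overall type I error.** Simulated with normal data, 32 per arm. Nominal per-pair coverage is 98.1% and nominal simultaneous coverage 95%.

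| SDs | A-B | A-C | Simultaneous | ANOVA type I error |
|---|---|---|---|---|
| 1:1:1.5 | 99.4% | 97.1% | 94.7% | 5.4% |
| 1:1:2 | 99.9% | 96.3% | 94.0% | about 6% |
| 1:1:3 | 100.0% | 95.3% | 93.4% | about 7% |

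At 29 per arm the picture is the same. Unequal loss can worsen it: with 32/32/24 analysed (assumed) and SDs 1:1:2, the A-C ratio falls to 0.82 and type I error rises to 8.3%.

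**Step 3: A-B power, adjusted test against adjusted test.** In the first four rows the true A-B difference is 0.8 times A's SD.

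| Assumption | Tukey after ANOVA | Games-Howell |
|---|---|---|
| SDs 1:1:1 | 79% | 78% |
| SDs 1:1:1.5 | 63% | 78% |
| SDs 1:1:2 | about 43% | 78% |
| SDs 1:1.5:2 | 35% | 54% |
| Means 3, 4.2, 6; SD half the mean | 37% | 59% |

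**Step 4: after the change.** Welch's ANOVA has type I error of 5.0% at both 1:1:2 and 1:1:3. Games-Howell per-pair coverage is 97.8-98.3% for every pair in those two cases.

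**The case against.** **Direction.** A reader might infer that unequal spread makes A-B far too wide and A-C too narrow. The protocol does not support that. It needs C to be clearly the noisiest arm with A and B alike, and nothing in the text says so. If A is noisiest, both A contrasts are too narrow; if B is, the directions swap; at 1:2:2 both are too wide. A very wide A-B interval also needs an SD ratio near 2; at 1.5 the excess is 19%.

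**Size.** At 1:1:2 an unadjusted pooled t interval for A-C covers about 92%, and it is tempting to charge that to the plan. Tukey, the test the plan gives as its example, covers 96.3% against 98.1%, with simultaneous coverage 1 point below nominal. Likewise, in the scenario with SD half the mean, setting Tukey's 37% against the 73% of an unadjusted Welch t test mixes error rates. Like for like it is 37% v 59% adjusted, or 56% v 73% unadjusted. Equal allocation keeps the overall F test close to its level.

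**Shape.** Zero-bounded data with spread proportional to the mean are usually skewed, and the simulations are normal. With gamma data (an assumed shape) at those means and SDs, a Shapiro test rejects normality in at least one arm about 86% of the time, which would send the analysis to Kruskal-Wallis. This stands: the Tukey power losses describe only the ANOVA branch. But the rank branch does not cure unequal spread either.

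**Left open.** Tukey is only an example, the intervals are not defined as pooled contrasts, and a variance check is often left to an analysis plan, which is not shown here. This lowers the severity. It does not dispose of the point, because Section 10 itself names the method, its fallback and the trigger, and the trigger covers one assumption of two. Other post-hoc tests that use the ANOVA error term share the weakness.

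**Conclusion.** The point holds in limited form, at low to moderate severity. Section 10 names an equal-variance analysis and protects it only against non-normality. If spreads differ, pairwise comparisons are miscalibrated even with equal arms, and the larger harm is lost power between the quieter arms: about 15 to 35 points across the assumed scenarios (78 − 63 = 15 at 1:1:1.5; 78 − 43 = 35 at 1:1:2). The liberal side is modest with Tukey: interval widths fall short by 7-14% for pairs with a single noisiest arm at ratios of 1.5 to 3, and simultaneous coverage stays at 93.4% or above with equal arms.

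All of this rests on assumed SDs and normal data. The documents do not show that any arm is more variable, so they support neither a claim about a particular contrast nor a claim that the trial's results would be wrong.

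**What to change.** In Section 10, replace ANOVA and Tukey with Welch's ANOVA and Games-Howell comparisons, or Welch contrasts under whatever multiplicity rule is adopted, for the continuous and scored outcomes. State that the 95% intervals are for differences between arms and use the same unpooled standard errors. If the switch to Kruskal-Wallis is kept, do not present it as protection against unequal spread.

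The cost is a sentence or two. If the SDs are in fact equal, power falls by about 0.5 to 1 point (78.3-78.6% against 79.0%). Where one arm is noisier, pairs that include it get wider intervals, by about 12% at 1:1:2 (1/0.894 = 1.12), and so lower power. That is the honest precision for those pairs, not a loss caused by the method.

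### Section 8 gives its 5% type I error, 80% power and 96 patients to the complication rate, which is none of the four primary outcomes in Section 7

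*Protocol*

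**What the plan says.** **Section 7 (Outcome Measures).** Under "Primary Outcome Measure" it numbers four outcomes without ranking them: operation time, intraoperative bleeding, healing time and intra-operative pain. The secondary list begins with "5. other complications", reported as an incidence rate, followed by patient satisfaction. Primary outcome 4 has a one-day time frame, but its description adds "while the post-operation pain was graded at 1 week by NRS (Numeric Rating Scale").

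**Section 8 (Sample Size Calculation).** With alpha 0.05 and beta 0.20, "a power of 80% is desired to detect a significant difference in the primary outcome (complication rate"). The total is 96, or 32 per group, and "This sample size assumes a 10% dropout rate, so 96 patients will be recruited in total". No complication rates and no effect size are given.

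**Section 10 (Statistical Analysis).** "P-values of < 0.05" is the general threshold for significance. The one multiple-comparison step is a post-hoc test such as Tukey's after a significant ANOVA. It acts across the three groups within an outcome.

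**The concern.** The sample size is the only place where the protocol ties an error rate and a power to a named outcome. That outcome is not among the primaries, and complications appear in Section 7 only at the secondary level. A reader cannot tell which result the 5% and the 80% are meant to support.

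If Section 7 governs, the trial has four primary outcomes with no stated power for any of them, each compared with 0.05. If Section 8 governs, there is one primary outcome, and the four results under the primary heading are secondary. The two readings lead to different confirmatory conclusions from the same data.

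**Working it through.** **1. The plan's own figure.** The total of 96 cannot be reproduced, because Section 8 gives no complication rates. The dropout arithmetic gives 96 × 0.9 = 86.4, so about 86 evaluable patients (28.8 per group), if dropout reaches the stated 10%.

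**2. The sections side by side.**

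| Outcome | Section 7 | Section 8 |
|---|---|---|
| Operation time | primary | not mentioned |
| Intraoperative bleeding | primary | not mentioned |
| Healing time | primary | not mentioned |
| Intra-operative pain | primary | not mentioned |
| Complications | secondary | the primary; carries alpha 0.05, power 80%, n = 96 |

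No outcome is primary in both sections.

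**3. Conditional illustration of the error rate.** Assume no true difference on any outcome, one overall three-group test per outcome at 0.05, and a claim allowed on any one of the four.

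- Independent tests: 1 − 0.95⁴ = 0.1855, or 18.5%.
- Lower limit, tests that coincide completely: 5%.
- Upper limit under any dependence: 4 × 0.05 = 20%.
- Simulated one-way ANOVAs (40,000 runs, 29/29/28 patients, equally correlated normal outcomes) at assumed correlations 0.3, 0.5 and 0.7: 17.8%, 15.8% and 13.4%. The protocol gives no correlations.

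If instead all four must be significant, the chance of a false claim is at most 5%.

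**4. What Holm's procedure does and costs.** The ordered P-values are compared with 0.05/4 = 0.0125, 0.05/3 = 0.0167, 0.05/2 = 0.025 and 0.05. The familywise error of the four overall tests is then at most 5% under any dependence. In the simulation it was 4.9% at correlation 0 and 3.9% at 0.7.

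The noncentral F distribution with three groups and N = 86 gives 80% power at f = 0.341 for alpha 0.05 and at f = 0.404 for alpha 0.0125. An effect of f = 0.341 has power 61%, 65% and 71% at 0.0125, 0.0167 and 0.025. These f values are generic, since the protocol states no effect size.

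**5. Pairwise claims under Holm.** The objective is Group A against Groups B and C, so the post-hoc tests matter as much as the overall ones. Suppose A and B are the same and only C differs, strongly, on all four outcomes. Holm then correctly rejects all four overall tests, and Tukey's test at 0.05 follows for each.

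- The critical value is q = 3.375 on 83 degrees of freedom, so |t| > 3.375/√2 = 2.386. The false A-versus-B rate is about 1.93% per outcome.
- Over four outcomes: 1 − (1 − 0.0193)⁴ = 7.5% if independent, and at most 4 × 0.0193 = 7.7%.

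Holm on the overall tests therefore does not by itself hold the pairwise claims at 5%. Tukey at 0.0125 per outcome does, since 4 × 0.0125 = 0.05.

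**6. If the complication rate is the one primary.** Power of a three-group chi-square test at 28.8 per group, with rates assumed for illustration: 21% for 5/15/15%, 36% for 5/20/20%, 66% for 5/30/30% and 78% for 5/35/35%.

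**The case against.** The strongest objection is that a success rule and a multiplicity procedure are commonly left to the statistical analysis plan, which is not shown, and that a general 0.05 threshold is not wrong in itself. That stands. The absence of an adjustment is not the finding, and the 18.5% is only an illustration. A reader might infer from it that the trial's false-positive rate is 18.5%. The protocol does not support this, because it never says that any one outcome suffices. Independence is also unlikely for operation time, bleeding and pain recorded at the same operation.

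Two further extensions are tempting and should be left out. One counts the one-week pain score as a fifth primary test. The title and time frame of outcome 4 both exclude that score, and no separate test of it is stated. The other says healing time is tested twice: Section 10 has "Analysis of variance (ANOVA) will be applied to compare continuous variables (e.g., healing time, pain scores) between groups", and also Kaplan-Meier analysis, which "will be used to assess time to healing (i.e., complete wound closure"). No test is named with Kaplan-Meier, so it may be a descriptive display beside the ANOVA.

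The objection does not remove the contradiction between Sections 7 and 8. An analysis plan can choose between them but cannot make both true.

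**Conclusion.** Sections 7 and 8 name different primary outcomes, and the stated alpha, power and sample size apply to none of the four that Section 7 lists. This rests on the text alone and needs no assumption. It should be fixed.

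The size of any error inflation is conditional. If one significant outcome is enough, it lies between 5% and 20%: 18.5% with independence and about 13% to 18% at assumed correlations of 0.7 to 0.3. If all four are required, it is at most 5%. The protocol states neither rule. Whether 96 patients are enough can be neither confirmed nor refuted, because Section 8 gives no rates.

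**What to change.** Make Sections 7 and 8 name the same primary outcome or outcomes. Section 12 gives an end date of 2024-2-07 and Section 7 describes several measurements in the past tense, so the choice should be made, and documented as made, without reference to results already seen. Restate Section 8 as the effect detectable with the fixed 96 patients (about 86 after dropout). No increase in enrolment is proposed.

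**Option 1: one primary.** For example, list the complication rate, on which Section 8 is already based, as the primary outcome in Section 7, with one overall three-group test at 0.05. The present four become secondary. *Cost:* those four no longer carry the claim, and at this size only large differences in complication rates are detectable (working, step 6). If a continuous outcome is chosen instead, Section 8 needs a new basis.

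**Option 2: four primaries.** Limit outcome 4 to the one-day intra-operative score and make one-week pain secondary. In Section 10, judge the four overall tests by Holm's procedure at a familywise 5%. Allow post-hoc tests only for outcomes rejected, at a level that also keeps the A-versus-B and A-versus-C claims within 5% across the four outcomes, for example Tukey at 0.0125 per outcome. Restate Section 8 for these outcomes. *Cost:* the detectable ANOVA effect rises from f = 0.34 to 0.40 at the first Holm step, and pairwise power is lower.

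Both options are changes of text.
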